#### 5.1.6 **Enthesitis: Leeds Enthesitis Index**

In the evaluation of MDA-Joints, enthesitis will be assessed by the Leeds Enthesitis Index (LEI) (Appendix G of Protocol).

For the LEI, pain will be assessed at the following 6 entheses (tendon insertions) sites: Lateral epicondyle humerus (left/right (L/R)); Medial condyle femur (L/R); and Achilles tendon insertion into calcaneum (L/R). Tenderness at each site is quantified on a dichotomous basis: 0 means nontender and 1 means tender. The LEI ranges from 0 to 6.

Data resource: LEI is entered by the physician via tablets provided by ERT.

Protocol Number: 20200058

Date: 07 February 2023

Page 24 of 67

#### 5.1.7 BSA

BSA (Appendix H of Protocol) is a measurement of involved skin. The overall BSA affected by psoriasis is estimated based on the palm area of the subject's hand (entire palmar surface or "handprint"), which equates to approximately 1% of total body surface area. All subjects will have their BSA assessed by the Evaluator.

Data resource: BSA is entered by the physician via tablets provided by ERT.

#### 5.1.8 Physician's Global Assessments of Disease Activity

The Physician's (Evaluator's) Global Assessments of Disease Activity is an assessment of how active a subject's psoriatic arthritis was on average during the last week. For the Physician's (Evaluator's) Global Assessments of Disease Activity, evaluator should mark a single vertical mark on a 100-mm VAS, with zero representing the lowest level of disease activity or pain and 100 representing the highest. The distance from the mark to the left-hand boundary of the scale will be recorded in millimeters.

Data resource: This VAS is entered by the physician via tablets provided by ERT.

# 5.1.9 Enthesitis

In addition to assessment by the Leeds Enthesitis Index, enthesitis will also be assessed

#### 5.1.10 Dactylitis

Dactylitis assessment will be done at screening, only a binary evaluation is needed (yes/no).

Protocol Number: 20200058 Date: 07 February 2023

# 5.1.11 Clinical Disease Activity Index for Psoriatic Arthritis (cDAPSA)

The cDAPSA score (Appendix K of Protocol) is based on the numerical summation of 4 disease activity variables: tender and swollen joints, subject's (patient's) global assessments of disease activity (SGA) and Subject's assessment of pain on a 10 cm Visual Analogue Scale (VAS).

cDAPSA = SJC(66)+TJC(68)+SGA(VAS 0-10 cm)+Pain(VAS 0-10 cm), with range of 0-154, and it will be set to missing if any of the 4 components is missing. A higher score indicates greater disease activity. Disease activity based on cDAPSA will be categorized as remission if cDAPSA  $\leq$  4, low disease activity if 4 < cDAPSA  $\leq$  13, moderate disease activity if 13 < cDAPSA  $\leq$  27, and high disease activity if cDAPSA > 27. The calculation of the cDAPSA will be performed programmatically.

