# 2. Objectives, Endpoints and Hypotheses

# 2.1 Objectives and Endpoints/Estimands

Objectives	Endpoints			
Primary				
To evaluate the efficacy of apremilast 30 mg BID ± NSAIDs and/or csDMARDs vs. Placebo ± NSAIDs and/or csDMARDs in subjects with early oligoarticular psoriatic arthritis (PsA), assessed by modified MDA (MDA-Joints).	
 
Proportion of subjects who achieve a clinical state of minimal disease activity (MDA-Joints) at Week 16, which is defined as achieving SJC ≤ 1 and TJC ≤ 1 (based on sentinel joints), plus 3 out of the following 5 criteria:         
 
Psoriasis BSA ≤ 3%;
 
Patient pain (VAS) ≤ 15;
 
Patient global disease activity (VAS) ≤ 20;
 
HAQ-DI ≤ 0.5;
 
Tender entheseal points ≤ 1 (based on Leeds Enthesitis Index - LEI)
 
 
 
			
Secondary				
To evaluate the impact of treatment with apremilast 30 mg BID ± NSAIDs and/or csDMARDs vs. Placebo ±NSAIDs and/or csDMARDs on disease activity in	cDAPSA remission or low disease activity: Proportion of subjects who achieve remission (defined by clinical disease activity in psoriatic arthritis [cDAPSA] ≤ 4 score) or low disease activity			

Page 9 of 67

Protocol Number: 20200058

Date: 07 February 2023 Page 10 of 67

subjects with early oligoarticular (defined by cDAPSA > 4 but  $\leq$  13 PsA. score) at week 16.

- Swollen Joint Count (SJC)  $\leq 1$ : Proportion of subjects with SJC ≤ 1 at week 16, based on sentinel joints.
- Tender Joint Count (TJC)  $\leq 1$ : Proportion of subjects with TJC ≤ 1 at week 16, based on sentinel joints.
- Patient's global assessment of disease activity: Proportion of subjects whose global assessment of disease activity score ≤ 20 in the visual analogue scale (VAS) at week 16.
- Patient's assessment of pain: Proportion of subjects whose assessment of pain score ≤ 15 in VAS at week 16.
- PASDAS good and moderate response: Proportion of patients achieving a good or moderate response in PASDAS score (Table 1) at week 16.
- To evaluate the impact of apremilast 30 mg BID ± NSAIDs and/or csDMARDs vs. Placebo ± NSAIDs and/or csDMARDs on patient-reported outcomes (PROs) in subjects with early oligoarticular PsA.
- PsAID-12: Change from Baseline in the Psoriatic Arthritis Impact of Disease 12-item for clinical trials (PsAID-12) questionnaire at week 16.

[figure not shown]

Protocol Number: 20200058 Date: 07 February 2023

Date: 07 February 2023 Page 11 of 67

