#### 5.1.12 Psoriatic Arthritis Disease Activity Score (PASDAS)

The PASDAS (Appendix L of Protocol) is a weighted index comprising assessments of joints, function, acute-phase response, quality of life (QOL), and patient and physician by VAS. The calculation of the PASDAS will be performed programmatically using the formula below:

PASDAS =  $((0.18 \times \sqrt{Physician global VAS}) + (0.159 \times \sqrt{Patient global VAS}) - (0.253 \times \sqrt{SF36-PCS}) + (0.101 \times LN (Swollen joint count + 1)) + (0.048 \times LN (Tender joint count + 1)) + (0.23 \times LN (Leeds Enthesitis Count + 1)) + (0.377 \times LN (Dactylitis count + 1)) + (0.102 \times LN (CRP + 1) +2))*1.5.$ 

Note: LN = natural logarithm, SF36 = Medical Outcomes Study Short Form-36, SF36-PCS = physical component summary scale of SF36, CRP = C-reactive protein in mg/L. High sensitivity C-reactive protein (hsCRP) and rheumatoid factor will be analyzed at a central laboratory.

All VAS scores are 0–100 mm. Swollen joint count is based on 66 joints, and tender joint count based on 68 joints. The score range of the PASDAS is 0–10, with worse disease

Page 25 of 67

Protocol Number: 20200058 Date: 07 February 2023

Page 26 of 67

activity represented by higher scores. If CRP is reported as below detection limit, then the value of detection limit will be used for PASDAS calculation.

If one or more components are missing, then PASDAS is set to be missing.

Table 1. Response criteria for the PASDAS

		Improvement	
Final PASDAS Score	≥ 1.6	< 1.6 but > 0.8	≤ 0.8
≤ 3.2	1	2	3
> 3.2 but < 5.4	2	2	3
≥ 5.4	2	3	3

1= good response; 2= moderate response; 3=poor response

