#### 9.5 Efficacy Analyses

#### 9.5.1 Analyses of Primary Efficacy Endpoint

The primary efficacy endpoint, proportion of subjects who achieve the modified MDA (MDA-Joints) at Week 16, will be compared between the Apremilast 30 mg BID group and placebo group using the Cochran-Mantel-Haenszel (CMH) test, controlling for use of glucocorticosteroids at baseline (yes/no) and use of a csDMARD (naïve, prior use only, or prior and concomitant use). Unadjusted group responder rates, unadjusted treatment differences in proportions, and adjusted treatment differences in proportions using the weighted average of the treatment differences across the strata with the CMH weights, along with the associated 2-sided 95% CIs using a normal approximation to the weighted average and the 2-sided p-values from the CMH tests, will be provided. Apremilast will be declared efficacious if the test result for the comparison is statistically significant in favor of Apremilast.

Subjects who have discontinued prior to Week 16 due to lack of efficacy or adverse event will be treated as non-responders in the analysis; and the multiple imputation methodology will be utilized, as appropriate, to impute the data for subjects whose

Page 49 of 67

event.

Protocol Number: 20200058 Date: 07 February 2023

modified MDA at Week 16 is missing for a reason other than lack of efficacy or adverse

The combination of non-responder imputation of some subjects and the multiple imputation of the rest of missing values at Week 16 is to address the Missing Not At Random (MNAR) nature of missing values at the analysis time point. The detailed data handling and analysis follow the procedures below:

Step 1. Censor or apply NRI (non-responder imputation) per different scenario

- (Censoring) After applying Early Termination Visit data, missing Week 16 values remain as missing for patients discontinued prior to Week 16 due to other reasons
- (NRI) Set non-responder (NR) to subjects discontinued prior to Week 16 due to
  - Lack of efficacy
  - Adverse event

Step 2. Implement multiple imputation, with 40 iterations (using fully conditional specification to impute the missing modified MDA generated from Step 1).

Step 3. Calculate statistics on each imputation iteration from Step 2.

Step 4. Combine results from Step 3.

The overall p-value will be derived from the CMH test that is normalized *via* the Wilson-Hilferty transformation (Wilson & Hilferty, 1931; Goria, 1992).

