#### Sensitivity analysis

Subjects with no response data to determine the response status at all assessment timepoints will be excluded.

The effect of protocol compliance will be studied by repeating the primary analysis using the PP population, according to the treatment subjects actually receive and the stratification factors subjects' medication data show.

In order to investigate the impact of the imputation method used for the primary analysis, a sensitivity analysis will be performed using the non-responder imputation for subjects who have discontinued prior to Week 16, or do not have sufficient information for a definitive determination of the modified MDA (MDA-Joints) status at Week 16. The responder analysis using the CMH model as in the primary analysis will be repeated.

Page 50 of 67

Protocol Number: 20200058 Date: 07 February 2023

To examine the robustness of the results obtained from the primary analysis based on the CMH method, a sensitivity analysis will be implemented using logistic regression. The responder analysis based on the logistic regression model will include treatment group, concomitant use of glucocorticosteroids at baseline (yes/no), and use of csDMARD (naïve, prior use only, or prior and concomitant use) as factors. This analysis will be based on the FAS data set used for the primary analysis with non-responder imputation along with the MI.

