### 9.5.2 Analyses of Secondary Efficacy Endpoint(s)

For the secondary endpoints, the missing data of the binary response parameters will be imputed using the non-responder imputation (NRI) and MI, as appropriate. The binary responses in the Placebo-controlled Phase will be analyzed using the CMH method, adjusted for use of glucocorticosteroids at baseline (yes/no) and use of a csDMARD (naïve, prior use only, or prior and concomitant use).

A mixed-effect model of repeated measures (MMRM) will be used to analyze the continuous endpoints. Because of the nature of the MMRM method, data from all timepoints during the Placebo-controlled Phase will be included in the model. Data obtained after early escape for subjects who escape early at Week 16 will be set to missing. Change from baseline will be analyzed using the MMRM approach with treatment group, time, treatment-by-time interaction, use of glucocorticosteroids (yes/no), use of csDMARD (naïve, prior use only, or prior and concomitant use) as factors, and baseline value as a covariate. Time will be treated as a categorical variable in the MMRM model. An unstructured covariance matrix will be used to model the within subject covariance. If the MMRM model using an unstructured covariance matrix fails to converge with the default Newton-Raphson algorithm, the Fisher scoring algorithm or other appropriate methods can be used to provide initial values of the covariance parameters. In the rare event that none of the above methods yields convergence, a structured covariance such as heterogeneous Toeplitz and Toeplitz structures will be used to model the correlation among repeated measurements. In this case, the empirical option will be used because the sandwich variance-covariance estimator is asymptotically consistent. Within-group least-squares (LS) mean changes from baseline, the associated standard errors (SEs) and 2-sided 95% Cls, treatment differences in LS mean changes from baseline at Week 16 and the associated 2-sided 95% CIs and 2-

[figure not shown]
Page 51 of 67

Protocol Number: 20200058
Date: 07 February 2023
Page 52 of 67

sided p-values will be obtained from the MMRM model and will be provided in the summary table.

All analyses on endpoints including joint counts will be performed on those joints that are affected at baseline (defined as sentinel joints).

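### cDAPSA and PASDAS are set to missing when any component is missing, so a response already determined by the observed components is imputed instead

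*SAP*

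**What the plan says.** SAP 5.1.11 gives the score as "cDAPSA = SJC(66)+TJC(68)+SGA(VAS 0-10 cm)+Pain(VAS 0-10 cm), with range of 0-154", "and it will be set to missing if any of the 4 components is missing". SAP 5.1.12 has the parallel rule for its eight-component score: "If one or more components are missing, then PASDAS is set to be missing".

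Both scores feed tested binary endpoints. The first secondary in SAP 2.1 is "cDAPSA remission or low disease activity: Proportion of subjects who achieve remission" or low disease activity at Week 16, which amounts to cDAPSA ≤ 13. PASDAS good or moderate response is the sixth. SAP 9.1.3 tests the secondaries in the order of Section 2.1 and stops at the first p-value of 0.05 or more.

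For secondary endpoints, SAP 9.5.2 says "the missing data of the binary response parameters will be imputed using the non-responder imputation (NRI) and MI, as appropriate". It does not say which missing values go to which method. The primary analysis in SAP 9.5.1 reserves non-responder imputation for discontinuation before Week 16 for lack of efficacy or adverse event. It uses multiple imputation for subjects whose "modified MDA at Week 16 is missing for a reason other than lack of efficacy or adverse" event. If that split carries over, a subject who attends Week 16 with one component missing goes to multiple imputation.

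**The concern.** A threshold on a sum of non-negative terms can be decided before every term is known. Where it is decided, the outcome is observed in all but name, and the plan discards it. Under multiple imputation, a certain failure can be drawn as a success or the reverse. The primary procedure imputes the binary status itself, and nothing in 9.5.1 or 9.5.2 makes the draws agree with the observed components. Under non-responder imputation, a certain success is counted as a failure.

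The plan is also uneven across endpoints. Patient global ≤ 20 mm and pain ≤ 15 mm are themselves tested secondaries. A subject with pain 75 mm and global 70 mm is an observed failure on both, yet is missing on cDAPSA, although those two values prove failure there too. HAQ-DI (6 of 8 categories suffice) and PsAID-12 (one missing item is filled) both have partial-data rules.

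At stake is some avoidable imputation noise, and possibly some bias, in two tested endpoints. One of them must be passed before any later secondary can be claimed.

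**Working it through.** **Component limits.** The SAP's range for cDAPSA reproduces: 66 + 68 + 10 + 10 = 154. All terms are non-negative and each VAS term is at most 10.

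**Bounds for cDAPSA ≤ 13, using 66/68 counts.** A subject is a certain non-responder if the observed sum exceeds 13. A subject is a certain responder if the observed sum plus the maximum of the missing terms is ≤ 13.

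- One VAS missing: certain responder if the other three sum to ≤ 13 − 10 = 3; certain non-responder if they sum to > 13.
- One or both joint counts missing: never a certain responder (13 − 66 and 13 − 68 are negative); certain non-responder if the observed sum is > 13.
- Both VAS missing: never a certain responder (13 − 20 is negative); certain non-responder if SJC + TJC > 13.

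Examples:

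- Joint counts missing, pain 7.5, global 7.0: at least 14.5, non-responder.
- SJC 0, TJC 1, global 1.5, pain missing: at most 0 + 1 + 1.5 + 10 = 12.5, responder.
- SJC 4, TJC 4, global 6.0, pain missing: at least 14.0, non-responder.

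SAP 5.1.11 makes all three missing.

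**PASDAS with CRP missing.** The CRP term is 1.5 × 0.102 × ln(CRP + 1), which is never negative and has no upper limit. Setting it to zero therefore gives the lowest possible Week 16 score and the greatest possible improvement, so only a poor response can be certain.

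Invented values, in the order physician global, patient global, SF-36 PCS, SJC, TJC, LEI, dactylitis, CRP:

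- Baseline (50, 50, 35, 3, 3, 2, 1, 5): 5.71.
- Week 16 (55, 60, 34, 4, 4, 3, 1, CRP missing): 5.87 with CRP 0, 6.23 with CRP 10, 6.57 with CRP 100.
- Improvement: −0.16, −0.53 and −0.87. The response is poor in every case.

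Other components can also leave PASDAS settled. From the same baseline, Week 16 values (9, 9, 48, 0, TJC missing, 0, 0, 2) give 2.06 to 2.37 as TJC runs from 0 to 68. The improvement is 3.64 to 3.34, a certain good response.

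**Size.** The documents give neither a rate of partly missing assessments nor expected cDAPSA rates. I assume that 1% to 10% of 285 subjects (about 3 to 29) are partly missing and settled, and I borrow the primary's 30% versus 15% for illustration.

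- Settled subjects resemble the rest of their arm: the expected difference stays at 15.0 points. Power with 190 and 95 subjects (2:1, before dropout) falls from 81.0% to 80.5% at 1%, or 76.4% at 10%.
- Extreme case, settled subjects are 3% of the apremilast arm only and are imputed at the rate of the rest of that arm. If all are non-responders, 0.30/0.97 = 30.9%, a difference of 15.9 points. If all are responders, (0.30 − 0.03)/0.97 = 27.8%, a difference of 12.8 points.

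**Why the imputation model must change as well.** Bounds settle non-responders under more missing patterns than responders. Suppose 60% of partly missing subjects truly respond and bounds settle 40% of the non-responders (both figures assumed). Settled failures are then 0.40 × 0.40 = 16% of the group and 84% is undetermined. Imputing that 84% at the overall 60% gives 0.84 × 0.60 = 50.4% responders instead of 60%. Bounds followed by imputation that ignores the observed components would pull response rates down.

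**The case against.** The strongest reply is that requiring every component is a clear, prespecified rule applied identically in both arms, and that few subjects will be affected. SAP 5.1.2 carries forward individual joints that cannot be assessed, so these do not make a joint count missing, and the efficacy components are entered on tablets. This limits the size of the problem but does not answer it, because no carry-forward exists for a lost VAS or hsCRP value or for a joint examination not done. The protocol's Table 13 footnotes foresee telemedicine visits replacing on-site ones, where such losses are plausible, though no rate is given.

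Two stronger readings are tempting and should not be drawn.

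- A reader might infer that cDAPSA is handled worse than the primary, because the plan speaks of a "definitive determination of the modified MDA (MDA-Joints) status at Week 16". That wording appears only in the primary's non-responder sensitivity analysis (SAP 9.5.1, protocol 9.6.3). The main primary analysis has no component-level rule either.
- A reader might infer a bias in a known direction. Both certain responders and certain non-responders are lost. Under non-responder imputation a certain non-responder is still counted correctly, and the SAP does not say which method applies.

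A simple repair can also do harm. If only missing VAS values were given their maximum, a subject with both joint counts missing and pain and global of 1.0 each would score 2.0 and be called a responder, although the counts could add up to 134. On that point the present rule is the safer one.

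**Conclusion.** The point holds as a small, correctable fault in the derivation rules. The text is unambiguous, and the bounds show that certain cDAPSA responders and non-responders, and certain PASDAS responses, are replaced by imputed values. The number affected is unknown and probably small, and the direction of any bias is not established. The power and difference figures rest on assumed rates of settled missingness and borrowed response rates. They show scale, and the one-arm cases are extremes.

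Two other matters bear on the bounds. SAP 5.1.11 uses 66/68 counts, whereas SAP 9.5.2 restricts joint-count endpoints to sentinel joints. With sentinel counts a missing joint count is capped by the number of sentinel joints, so more subjects would be certain responders. The PASDAS boundary also differs: SAP Table 1 calls an improvement of exactly 0.8 poor, whereas protocol Appendix L allows it to count as moderate when the final score is below 5.4.

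**What to change.** In SAP 5.1.11: *cDAPSA response (≤ 13) is non-response if the sum of the observed components exceeds 13. It is response if both joint counts and one VAS are observed and their sum plus 10 for the missing VAS is ≤ 13. Otherwise it is undetermined.*

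In SAP 5.1.12: *If only CRP is missing at Week 16, response is poor when baseline PASDAS minus the Week 16 score computed with the CRP term set to zero (keeping the +2 constant) is < 0.8, or when that score is ≥ 5.4 and that improvement is < 1.6. Otherwise it is undetermined.* Both conditions are safe under either version of the response table, but the 0.8 boundary should be reconciled.

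In SAP 9.5.2:

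- Send only undetermined cases to imputation and state which get non-responder imputation and which multiple imputation. Say how this fits with the rule in 9.5.1 that assigns non-response after discontinuation for lack of efficacy or adverse event.
- Impute the missing component within its possible range, or condition on the observed components, and then derive the response. Draws then cannot contradict observed data, and one-sided settling does not distort the rates. Imputing components within their range also covers PASDAS components other than CRP.
- State whether cDAPSA uses 66/68 or sentinel counts.
- Report settled and undetermined cases by arm.

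The cost is a few SAP sentences, some derivation code and a fuller imputation model, with no new data. It should be settled before the Week 24 database is unblinded.

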#### 5.1.12 Psoriatic Arthritis Disease Activity Score (PASDAS)

The PASDAS (Appendix L of Protocol) is a weighted index comprising assessments of joints, function, acute-phase response, quality of life (QOL), and patient and physician by VAS. The calculation of the PASDAS will be performed programmatically using the formula below:

PASDAS =  $((0.18 \times \sqrt{Physician global VAS}) + (0.159 \times \sqrt{Patient global VAS}) - (0.253 \times \sqrt{SF36-PCS}) + (0.101 \times LN (Swollen joint count + 1)) + (0.048 \times LN (Tender joint count + 1)) + (0.23 \times LN (Leeds Enthesitis Count + 1)) + (0.377 \times LN (Dactylitis count + 1)) + (0.102 \times LN (CRP + 1) +2))*1.5.$ 

Note: LN = natural logarithm, SF36 = Medical Outcomes Study Short Form-36, SF36-PCS = physical component summary scale of SF36, CRP = C-reactive protein in mg/L. High sensitivity C-reactive protein (hsCRP) and rheumatoid factor will be analyzed at a central laboratory.

All VAS scores are 0–100 mm. Swollen joint count is based on 66 joints, and tender joint count based on 68 joints. The score range of the PASDAS is 0–10, with worse disease

Page 25 of 67

Protocol Number: 20200058 Date: 07 February 2023

Page 26 of 67

activity represented by higher scores. If CRP is reported as below detection limit, then the value of detection limit will be used for PASDAS calculation.

If one or more components are missing, then PASDAS is set to be missing.

Table 1. Response criteria for the PASDAS

		Improvement	
Final PASDAS Score	≥ 1.6	< 1.6 but > 0.8	≤ 0.8
≤ 3.2	1	2	3
> 3.2 but < 5.4	2	2	3
≥ 5.4	2	3	3

1= good response; 2= moderate response; 3=poor response

